**VII.D.15 Check all materials that will be used to obtain/document informed consent:**

- Consent Document

**VII.D.16 Are you requesting a waiver of documentation of consent (either no subject signature or no written document)?**

No

**VII.D.19 Before the subject gives consent to participate are there any screening questions that you need to directly ask the potential subject to determine eligibility for the study?**

Yes

**VII.D.20 List any screening questions you will directly ask the potential subject to determine eligibility.**

Are you between 18 – 50 years of age?  
 How tall are you?  
 What do you weigh?  
 What racial/ethnic group do you self-identify with? (Subject will be provided a list of examples if clarification is required)  
 Do you have any general allergies that require daily treatment with steroids or antihistamines?  
 Have you ever had any kind of microneedle patch applied to your skin? If so, did you experience any adverse reactions to it?  
 Do you have a known allergy or adverse reaction to medical tape, Band-Aids, adhesive or aloe vera?  
 Do you take prescription medications?  
 Do you have any chronic or ongoing medical conditions (including skin disorders or pregnancy)?

Screening will be streamlined with the use of a redcap survey found at the following link. <https://redcap.icts.uiowa.edu/redcap/surveys/?s=4XJ8CYKNCF>

**VII.D.21 Will you keep a screening log or other record that would include information on people who do not enroll in the study?**

Yes

**VII.D.22 Describe the information being collected and the purpose for keeping this information.**

A screening log will be maintained that will document the first and last name of the prospective participant that was screened, date of screening, phone number if provided, email address if provided, and whether it was a screen failure or if the subject will continue on to the consent process. This information will be kept until all study activities have been completed for all participating subjects. We will keep the screening information because it is not uncommon for individuals to respond to the same advertisements more than once (for example, Noon News) and we want to know if a subject has previously contacted us about the study. The log will be destroyed when all subjects have finished the study.

**VII.D.23 Will this information be shared with anyone outside the UI research team members?**

No

**VII.D.25 After the subject agrees to participate (signs consent), are there any screening procedures, tests, or studies that need to be done to determine if the subject is eligible to continue participating?**

Yes

**VII.D.26 List and describe screening**

After a subject consents to be in the study, baseline demographic data will be collected including age, sex, height, and weight, race/ethnicity; information regarding current medical conditions/allergies and medications will also be collected. Specifically, the subject's approximate duration of each condition/allergy, what treatments the subject has received, and approximate severity of the conditions, and a current medication list will be collected. All of this information will be collected directly from the subject and the subject's medical record will not be reviewed/abstracted for research data.

**VII.D.27 Discuss how much time a potential subject will have to agree to consider participation and whether or not they will be able to discuss the study with family/friends before deciding on participation.**

There is no limit on the time a potential subject may take to consider participation. The only restriction on time is that the subject will only be allowed to participate if the study is still enrolling subjects when they provide consent.

**VII.D.28 How long after the subject agrees to participate do study procedures begin?**

Study procedures can begin immediately after obtaining consent.

**VII.D.29 Provide a description of the enrollment and consent process for adult subjects**

- **Describe each study population separately including control population**
- **Include when recruitment and consent materials are used**
- **Use 3rd person active voice “The Principal Investigator will identify subjects. For example, the principal investigator will identify potential subjects, the study coordinator will discuss the study with subjects over the telephone and schedule the first study visit, etc...”**
- **Describe the steps that will be taken by the research team to minimize the possibility of coercion or undue influence during the consent process**

This study will be advertised through the University of Iowa campus-wide email system and through the University of Iowa Health Care "Noon News," a daily announcement flier printed for community and faculty members within the UIHC. We will also be using printed fliers to advertise the study in [name] Skin Care Clinic at UIHC and on the University Campus System. The UIHC Clinical Trials and Research Website will be utilized for recruiting subjects. Subjects will be recruited through the dermatology clinic based upon screening of the EMR as well as by physician referral. Advertisements will also be hung in the University Services Building and various cultural centers on the University campus (African-American Cultural Center, Latino and Native American Cultural Center, and Asian-Pacific American Cultural Center). Advertisements for this study have been created so that specific subject populations may be better reached via targeted advertisements, in order to meet our enrollment goals. The mass mailing advertisement has been written in this way as well. It is possible that the mass email will be distributed to certain listservs of University students/staff/faculty that meet our specific demographic criteria (specifically race and ethnicity); we will be working with ITS, the registrar and HR to build confidential lists of individuals who will receive this email. These lists will only be exchanged directly between ITS, HR, and the registrar. No member of the research team will have access to any information about individuals being emailed in this manner.

Individuals who call the study site will be provided a brief overview of the purpose and study procedures. Prospective participants may be pre-screened through a telephone survey or a survey link created by researchers using a data collection tool called RedCap. If a subject is interested in study participation and passes pre-screening procedures, they will be invited to sign an informed consent with a study team member (where they will again be provided overview of the study rationale, procedures, risks, and benefits). An informed consent document will be provided to the subject for review prior to any meeting. If the prospective participant cannot receive an informed consent by email, the individual will be invited to review the document with the study coordinator at UIHC, and must be given the option to schedule a separate meeting to sign the document. This ensures that the individual has the chance to review the material in the informed consent on their own time.

Individuals who contact [name] for information about the study will be provided with a brief description of the study. They will also be provided with an informed consent document for them to review on their own time and will be instructed to contact the study coordinator for more information. Individuals identified prior to their appointment in the dermatology clinic will be invited by their physician or a member of the study team to meet with the study team to learn more about the research opportunity. Prior to their appointments individuals that have been screened by members of the study staff will receive a letter in the mail giving them information about the study and notifying them that they may be eligible to participate in the study. The principal investigator of this study is planning to conduct multiple onsite studies involving microneedles; currently a similar study in production is 201701708. Participants from this study will be sent a letter or email with information about this study instructing them to reach out to the study team if they are interested in participation. There will be no follow up to anyone who is sent a letter or email that does not respond.

Screening for this study will be streamlined with the use of a survey created by the research team (link provided in VII.D.20). The link to this survey will be sent to potential subjects via the Noon News, Mass Email, and the Letter to prior subjects. Participants who complete the survey will provide their email address, and the study team will contact them in response to their answers. The information provided by the individual will be used to determine eligibility and will not be kept or stored by the researcher. All information collected for purposes of this study will be collected during an in-person visit with the potential subject.

It is recognized that the consent process must be carried out in an environment where no coercion is applied and where subjects can be adequately informed of the purpose, nature, procedures, risks and hazards of the study. One of the important features of our screening process is the ability for the prospective participant to review the informed consent on his/her own time, outside of the study site. This additionally demonstrates the reliability of the subject if they schedule a follow-up meeting to sign the informed consent.

**VII.D.37     *Does the study include any form of deception (e.g., providing participants with false information, misleading information, or withholding information about certain study procedures)?***

*Examples:*

- *Procedure includes a cover story that provides a plausible but inaccurate account of the purposes of the research.*
- *Participants will be provided with false information regarding the particular behaviors of interest in the research.*
- *Procedures include a confederate pretending to be another participant in the study.*
- *Participants will be told that the research includes completion of a particular task, when in fact, that task will not be administered.*
- *Study is designed to introduce a new procedure (or task) that participants are not initially told about.*
- *If yes, a waiver of informed consent must be requested under question IV.3.*

No

**VII.E. Project Description (E)**

**VII.E.1     *Will subjects be randomized?***

No

**VII.E.3     *Will any questionnaires, surveys, or written assessments be used to obtain data directly from subjects in this study?***

Yes

**VII.E.4     *List all questionnaires, surveys, written assessments and ATTACH each one to the application. (NOTE: You are NOT prohibited from attaching copyrighted materials to this application)***

There will be a pre-screening questionnaire and a screening questionnaire to collect information from the subjects. File name: Pre-Screening Questionnaire MCK, Screening Questionnaire MCK

A survey will be utilized to help determine an individuals eligibility to participate in the study. This survey can be found at <https://redcap.icts.uiowa.edu/redcap/surveys/?s=4XJ8CYKNCF>

**VII.E.5     *Does this project involve creating any audiotapes, videotapes, or photographs?***

No

**VII.E.6     *Provide a detailed description in sequential order of the study procedures following the consent process - DO NOT cut and paste from the Consent Document.***

*Describe study populations separately if they will be participating in different procedures - include CONTROL population if applicable.*

**DESCRIBE:**

- *What subjects will be asked to do/what happens in the study (in sequential order)*
- *The time period over which procedures will occur*
- *The time commitment for the subject for individual visits/procedures*
- *Long-term followup and how it occurs*

Following consent, a member of the study team will obtain the following demographic information directly from the subject: age, height, weight, and gender. A member of the study team will also identify the subject's Fitzpatrick skin type, and obtain a list of current medications and ongoing medical conditions. The subject will be asked to elaborate on the duration and severity of medical conditions and any treatments received. No medical records will be consulted to obtain or confirm this information. A member of the research team will use this information to screen out subjects meeting any of the exclusion criteria defined in VI.13. Subjects who pass the screening may proceed to the next step described below. Consent and screening procedures will take approximately 1 hour.

On Day 0 (may be the same day as consent is obtained), the subject will sit in a study room at the CRU for 30 minutes prior to any procedures. This allows the subject's skin to acclimate to the ambient environment in the study room (temperature, humidity). Following this acclimatization, the researcher will identify and mark with a marker 5 sites at each of the following 3 locations (for a total of 15 sites): upper arm, volar forearm, and abdomen. Hair may be clipped (but not shaved) at the sites if necessary. Noninvasive baseline measurements will be taken at each of the 15 sites as follows:

- Hydration will be measured by gently pushing a corneometer probe against the skin. The measurement will take less than 30 seconds at each site.
- Transepidermal water loss (TEWL) will be measured by resting a probe gently against the skin. This measurement will take 1-3 minutes at each site. (TEWL will only be measured on Day 0.)
- Electrical resistance (impedance) will be measured with an impedance meter by applying gel electrodes to each site and a reference electrode at a nearby site. The measurement will be repeated 3 times at each site, and will take less than 2 minutes total at each site.
- Skin color and redness will be measured by placing a colorimetry probe gently against each site. This measurement will take less than 30 seconds at each site.

Following baseline measurements on Day 0, micropatches will be applied to three of each set of five sites. The sites will first be cleansed with an alcohol swab. A sterilized micropatch containing 50 tiny projections, each 800 um in length, will be placed perpendicular to the skin, and the researcher will apply gentle pressure to the back of the patch for 10 seconds. The researcher will then remove the patch, rotate it 45 degrees, and apply it again at the same site for another 10 seconds. This will create 100 micropores at each site. Micropatch application will only occur on Day 0.

Immediately after treating a site with a micropatch, TEWL and impedance measurements will be repeated. The site will then be covered with a sterile occlusive cover, and the researcher will apply a new micropatch array to the next site. Two sites at each location will not receive micropatch treatment. An occlusive covering will be placed over one of these two sites, and the other untreated site will remain uncovered. The 4 covered sites will be secured with medical tape. Note that all baseline measurements, micropatch applications, Day 0 post-micropatch measurements, and covering and medical tape placement will be performed at one anatomical location (5 sites) before proceeding to the next location. Day 0 procedures will require 3 - 4.5 hours.

Subjects will be asked to return to the CRU every 24 hours for 3 days. On each day hydration, impedance, and color measurements will be repeated at all sites. New occlusive material will be applied on Days 1 - 2. On Day 3 (the final day), covering will be removed, but not replaced. Procedures on Days 1-3 will last 2 - 3 hours.

Within 3-4 days after the Day 3 visit (or the last completed visit if a participant decides to drop out early) a study team member will contact the subject via phone or email to determine if the subject is experiencing any redness or irritation at the treatment site. No long-term follow-up will be necessary. The overall time commitment for this study is 9 - 13.5 hours in one week, across 4 study days if consent is obtained on Day 0, or 5 study days if consent is obtained before Day 0; consent may occur any time prior to study procedures.

**VII.E.7** *Will you attempt to recontact subjects who are lost to follow-up?*  
No - those lost to followup will not be recontacted

**VII.E.9** *Will subjects be provided any compensation for participating in this study?*  
Yes

**VII.E.10** *Cash*  
No

**VII.E.11** *Gift Card*  
No

**VII.E.12** *Check*  
Yes

**VII.E.13** *Who will be providing the research compensation check to the subject?*  
Accounting Services directly via the e-Voucher system

**VII.E.16** *Other*  
No

**VII.E.19** *Describe the compensation plan including*

- *Compensation amount and type per visit*
- *Total compensation*
- *Pro-rating for early withdrawal from study*

Compensation will be provided as follows:

Day 0- \$100

Day 1- \$40  
 Day 2- \$40  
 Day 3- \$40  
 Total - \$220

Compensation will be prorated for any subject who does not complete all days of the study. Subjects will only be paid for the study days they complete. Subjects will be paid in one check.

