There are almost no data comparing microneedle response at different anatomical sites, and there are limited data available describing the variation in skin characteristics at different sites. The skin on the abdomen and forearm is more mature than skin on the cheek and wrist. Hispanic/Latino individuals and Caucasian/White individuals have higher water content on one surface of the forearm compared to another. There are also differences in skin thickness, water loss, and protein and lipid composition across sites that can impact drug migration to the systemic circulation. All commercially available transdermal patches are approved for application only at specific body sites because of the variation in drug absorption that can occur from application on other locations on the body. Though direct comparisons of skin response to microneedle application at various sites are lacking, it is reasonable to expect that these differences will affect the rate at which micropores close, thus also affecting the drug absorption at that site.

Data characterizing racial/ethnic structural differences in the skin barrier are also limited. When comparing African American/Black, Asian, and Caucasian/White individuals, skin maturity and barrier strength is greatest in the African American/Black population and weakest in the Asian population. African American/Black individuals also have greater electrical resistance compared to Caucasian/White individuals. Highly pigmented skin exhibits faster recovery compared to lighter pigmentation. These differences are important considerations in micropore closure across populations. A study is currently underway in this lab to explore the differences in microneedle response in various racial/ethnic groups, but that study will only address differences at a single anatomical site.

In this study we will apply microneedles to the abdomen, forearm, and upper arm, by using a micropatch, in five racial groups. These sites were chosen in consideration of patient-accessibility for future self-application of a micropatch. We will measure electrical impedance to evaluate micropore closure and water loss to represent skin barrier integrity. We will also measure hydration, and redness/color to

characterize skin differences in both location and race. The results of this study will provide insight into the optimal locations for microneedle-assisted transepidermal drug delivery in a diverse population.

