## XI. Data Analysis

**XI.1** *Describe the analysis methods you will use, including, if applicable, the variables you will analyze*  
Descriptive statistics will be used for subject demographics. Each subject will serve as their own control, and paired t-tests will determine differences in TEWL (water loss measurements) and impedance from baseline to post-microneedle insertion. This will be used to determine if the microneedles adequately breached the skin barrier, demonstrated by a significant increase in TEWL from baseline and a significant decrease in impedance from baseline. For the colorimetry, and hydration measurements, each daily measurement will be compared to its baseline at that site, as well as to its hydration control (untreated, occluded site), using paired t-tests.  
Impedance data will be analyzed using similar methods as our previous study, and will ultimately be used to calculate the half-life of micropore closure. Z-pores values will be calculated from impedance measurements taken immediately following and over the days following microneedle treatment. These values will be converted to admittance (the inverse of impedance), which can demonstrate how “open” the micropores are in a very intuitive manner. If a micropore has a maximum admittance, then the micropore is 100% open. Using this information, we will plot admittance vs. time and calculate a rate constant of micropore admittance (k). The rate constant is then used to calculate the half-life of micropore closure, which thus describes a rate of closure in units of time. This micropore half-life will serve as the primary endpoint and will be compared among locations within a group, among groups within a location, and among locations in all groups.

**XI.2** *Provide the rationale or power analysis to support the number of subjects proposed to complete this study.*  

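### Nothing sets which of the five positions at each location is treated, occluded or left bare, so the hydration and colour tests against the occluded control could carry a position difference

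*Combined protocol and SAP*

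**What the plan says.** Section VII.E.6 has the researcher mark five sites at each of the upper arm, volar forearm and abdomen, 15 in all, and take baseline readings at every one. It continues: "Following baseline measurements on Day 0, micropatches will be applied to three of each set of five sites". For the two sites left untreated: "An occlusive covering will be placed over one of these two sites, and the other untreated site will remain uncovered". The split at each location is therefore three treated, one occluded control and one bare.

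No section says how positions are matched to these conditions, who decides, or when. VII.E.1 ("Will subjects be randomized") is answered No, but that question concerns subjects, not positions within a subject. VII.B.11 states that no separate written protocol will be submitted, so the rule is not deferred to another submitted protocol.

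For colour and hydration, XI.1 plans two comparisons. In the first, "each daily measurement will be compared to its baseline at that site". In the second, the same daily measurement is compared with the control: "as well as to its hydration control (untreated, occluded site), using paired t-tests". The second is not described as adjusted for baseline.

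**The concern.** Treated sites receive both microneedles and up to three days of covering. For hydration and colour, a change from the site's own baseline mixes the two effects. The comparison with the untreated, occluded site is the one that pulls them apart, and there is one such site per location.

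If that control usually sits in the same place relative to the treated sites, any systematic difference in skin between those places enters the contrast with the same sign in every subject. More subjects do not average it away. They make the test more likely to declare it significant. A position difference would then be reported as a microneedle effect on hydration or colour, or would mask a real one. XI.2 describes the study as a pilot to inform a later power analysis, so a distorted contrast could carry over into that planning.

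**Working it through.** **Inputs.** Five positions per location, split 3:1:1 (VII.E.6). Target enrolment of 14 in each of 5 groups, with 10 per group expected to complete (VI.13). Paired t-tests (XI.1). The documents give no SD, no position effect, no alpha and no sidedness. I assume a two-sided 5% test and express the offset in SDs of the paired difference.

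**The plan's own figure.** 14 × 5 = 70 enrolled and 10 × 5 = 50 completers; 50 ÷ (10/14) = 70. The enrolment figure reproduces. It rests on feasibility, and nothing here changes it. It supplies n = 10 for a test within one group and n = 50 if all groups are pooled. XI.1 does not say that they will be pooled.

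**Which tests are exposed.** Write a reading as subject level + position effect + condition effect + error.

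| Planned comparison | Position effect |
|---|---|
| Hydration or colour: daily reading, treated versus occluded control | Remains: mean over treated positions minus control position |
| Hydration or colour: daily reading versus same-site baseline | A constant offset cancels |
| TEWL and impedance: baseline versus post-insertion | Baseline-to-post change; no control site named |
| Half-life among locations and groups (primary) | Not a treated-versus-control contrast |

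**Rejection rate with no microneedle effect.** Take one treated-minus-control difference per subject and a constant offset d. Then T follows a noncentral t with n − 1 degrees of freedom and noncentrality d√n. The rejection rate is P(|T| > critical value), with critical value 2.262 at n = 10 and 2.010 at n = 50.

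| d (assumed) | d√10 | Rejects, n = 10 | d√50 | Rejects, n = 50 |
|---|---|---|---|---|
| 0.1 | 0.316 | 0.059 | 0.707 | 0.107 |
| 0.3 | 0.949 | 0.136 | 2.121 | 0.548 |
| 0.5 | 1.581 | 0.293 | 3.536 | 0.934 |

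**What random positions would do.** There are 5!/(3!·1!·1!) = 20 layouts per location. If positions are numbered 1 to 5, the mean treated position minus the control position runs from −3 to +3 steps and averages 0 over the 20 layouts. A fixed layout with treated 1–3 and control 4 gives 2 − 4 = −2 steps. With an assumed linear gradient of 0.25 SD per step, that is an offset of 0.5 SD. In 20,000 simulated trials the fixed layout rejected in 0.298 (n = 10) and 0.932 (n = 50). Layouts drawn at random for each subject rejected in 0.049 and 0.052.

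Randomising turns the bias into noise. The position difference has an SD of 1.826 steps over the 20 layouts, so at 0.25 SD per step the SD of the paired difference rises from 1 to √(1 + (0.25 × 1.826)²) = √1.208 = 1.10. Analysing change from baseline also removes that part, provided the position effect is additive and stable over the days.

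**The case against.** The strongest reply is that this is silence in a self-described pilot and touches one secondary contrast. The primary half-life is compared among locations and groups. The breach check runs from baseline to post-insertion, and its post-insertion readings are taken before the site is covered, so occlusion does not confound it. Hydration and colour also have a same-site baseline comparison that cancels a constant offset. Baselines are taken at all 15 sites, so position differences could be checked or adjusted for. All of this stands, and it limits the reach. It does not protect the control comparison as XI.1 describes it, because that comparison uses the daily reading with no stated adjustment.

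A reader might infer more in three places.

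- **That the researcher chooses the treated sites after seeing the baseline readings.** The text does not say so. "Following baseline measurements on Day 0, micropatches will be applied to three of each set of five sites" gives the timing of application, not of assignment. A layout settled when the sites are marked, before baseline, fits the text equally well.
- **That the documents show a gradient among the five positions.** Section I.6 says that Hispanic/Latino and Caucasian/White individuals "have higher water content on one surface of the forearm compared to another". That compares surfaces, and all five forearm sites are volar. It is at most suggestive.
- **That the primary endpoint is biased.** It would be touched only if a control-site reading enters the Z-pores calculation, which XI.1 does not state.

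The rejection rates also need a layout that is constant across subjects. Positions that varied haphazardly would not produce a constant offset, and the rates would not apply.

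**Conclusion.** The concern holds in a limited form. The plan has no rule for assigning positions to conditions, and one planned contrast is exposed: treated versus occluded control for hydration and colour. Under an assumed constant offset of 0.1 to 0.5 SD, the false-positive rate runs from about 6% to 29% at n = 10 and from about 11% to 93% if 50 completers are pooled. At the low end with n = 10 the harm is negligible.

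These figures rest on assumptions that the documents neither support nor contradict: the size of the offset, a layout common to all subjects, a two-sided 5% level and, for the higher figures, pooling. The documents do not show that a bias exists or that anyone selected sites on their readings. They leave it unprevented where prevention is nearly free, so the change should be made.

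**What to change.** In VII.E.6:

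- Number the five positions at each location by anatomical landmark.
- Before any baseline reading, assign the conditions (three treated, one occluded control, one bare) from a pre-generated list. The list should randomise or rotate positions across subjects, separately for each location and balanced within each racial/ethnic group.
- Record the position of each condition on the case report form.

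In XI.1:

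- Compare treated and occluded-control sites on change from each site's own baseline, which is already collected.

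The cost is one allocation list and one case report form field. No visits, measurements or subjects are added.

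### The untreated, uncovered site has no comparator role in XI.1, so own-baseline tests of daily hydration and color at the covered sites mix visit-to-visit drift with any effect

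*Combined protocol and SAP*

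**What the plan says.** Section VII.E.6 lays out "5 sites at each of the following 3 locations (for a total of 15 sites): upper arm, volar forearm, and abdomen". On Day 0, "micropatches will be applied to three of each set of five sites". The other two sites at each location are untreated, and they differ only in the cover: "An occlusive covering will be placed over one of these two sites, and the other untreated site will remain uncovered".

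All sites are read before treatment ("Noninvasive baseline measurements will be taken at each of the 15 sites as follows"), and on Days 1-3 "On each day hydration, impedance, and color measurements will be repeated at all sites". Water loss is the exception ("TEWL will only be measured on Day 0"). The same section requires 30 minutes of acclimatization to room temperature and humidity on Day 0. The description of Days 1-3 does not repeat that step.

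For color and hydration, section XI.1 plans paired t-tests in which "each daily measurement will be compared to its baseline at that site, as well as to its hydration control (untreated, occluded site", the closing bracket following. That occluded site is the only concurrent control XI.1 names; the uncovered site is not mentioned there. The water-loss and impedance t-tests compare baseline with the reading after insertion. The primary endpoint, micropore half-life, is derived from impedance through a Z-pores calculation that follows an earlier study and is not written out.

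**The concern.** A test of a Day 1, 2 or 3 reading against the same site's Day 0 baseline takes in everything that changed between visits: needle, cover, room, instrument and subject. The uncovered site has neither needles nor cover, so its change is the only direct measure of the last three. The design collects that measure at each location and visit, but XI.1 does not set it against any other reading.

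Two things are at stake. A significant own-baseline change in hydration or color at a treated or occluded site could be reported as an effect when it is partly or wholly drift. And the effect of covering alone is not estimated, although both sites needed for it are measured. Covering matters for interpretation: section I.6 says that occlusion extends micropore life from about 2 hours to 48-72 hours and lists hydration among the characteristics that may affect healing.

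**Working it through.** **Reproducing the plan's count.** 5 sites × 3 locations = 15, as stated. Uncovered sites: 1 × 3 = 3, and 3/15 = 20%.

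**Share of readings, per location** (impedance counted once per site and visit)
- Days 1-3: 3 days × 5 sites × 3 measures = 45. The uncovered site gives 3 × 3 = 9, and 9/45 = 20%.
- All readings: baseline 5 × 4 = 20; post-patch water loss and impedance at treated sites 3 × 2 = 6; Days 1-3, 45. Total 71. The uncovered site gives 4 + 9 = 13, or 18.3%.
- If its hydration and color are tested against their own baseline, only its one water-loss and four impedance readings lack a stated use: 5/71 = 7.0%.
- Impedance is read in triplicate at baseline ("The measurement will be repeated 3 times at each site"). Assuming the same later, the last two shares become 21/117 = 17.9% and 13/117 = 11.1%.

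**What each comparison estimates.** Let D be drift common to the sites of a location between Day 0 and a later day, C the covering effect and N the needle effect.

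| Comparison (hydration, color) | Estimates | Role in XI.1 |
|---|---|---|
| Treated, change from baseline | D + C + N | planned |
| Occluded untreated, change from baseline | D + C | covered by the wording |
| Uncovered untreated, change from baseline | D | covered by the wording, as a stand-alone test |
| Treated minus occluded untreated, same day | N | planned |
| Occluded minus uncovered untreated, change | C | not stated |
| Treated minus uncovered, change | C + N | not stated |

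**Size of the drift problem (illustration).** Inputs from the documents: 10 completers in each of 5 groups, so 50 in all (VI.13, XI.2). XI.1 does not say whether the paired tests are run by group or pooled, so both sizes are shown. Assumed, because the documents give no value: two-sided alpha 0.05, C = N = 0, and a systematic drift of d SDs of the paired change. The rejection probability is P(|T| > t(0.975, n−1)), with T noncentral t on n−1 degrees of freedom and noncentrality d√n.

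| d | d√n, n=10 | Rejects, n=10 | d√n, n=50 | Rejects, n=50 |
|---|---|---|---|---|
| 0 | 0 | 5% | 0 | 5% |
| 0.2 | 0.63 | 9% | 1.41 | 28% |
| 0.3 | 0.95 | 14% | 2.12 | 55% |
| 0.5 | 1.58 | 29% | 3.54 | 93% |

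**After subtracting the uncovered site's same-day change.** A simulation (20,000 runs, between-site correlation of changes ρ = 0.5, drift common to both sites) gave rejection of about 5% at drifts of 0.2, 0.5 and 0.8 SD, for n=10 and n=50.

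**Noise cost.** For one covered site, the SD of the net change is √(2(1−ρ)) times the SD of the unadjusted change: 1.41 at ρ = 0, 1.00 at ρ = 0.5, 0.71 at ρ = 0.75. If three treated sites are averaged, the ratio is √[(1+2ρ)/3 + 1 − 2ρ] / √[(1+2ρ)/3]: 1.155/0.577 = 2.00 at ρ = 0, 0.816/0.816 = 1.00 at ρ = 0.5, and 0.577/0.913 = 0.63 at ρ = 0.75. Adjustment widens the interval when sites are weakly correlated and narrows it when they are strongly correlated.

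**The case against.** The case for leaving XI.1 alone has real force.

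- **The uncovered site may already be analyzed.** A reader might infer that it enters no analysis. The documents do not support that: the own-baseline comparison is not limited to treated sites, and the Z-pores inputs are not given, so use of untreated-site impedance cannot be ruled out. What stands is narrower. A separate test at the uncovered site shows drift but removes it from no other comparison.
- **A fifth of the data is not wasted.** A reader might infer so from the 20% figure. That figure describes sites and Day 1-3 readings; the share of all readings with no stated use may be only 7-11%.
- **The needle effect is already protected.** The same-day comparison with the occluded site cancels shared drift. Netting both sites against the uncovered one changes nothing, since (treated − uncovered) − (occluded − uncovered) = treated − occluded. The Day 0 water-loss and impedance tests span no visits. These points stand in full.
- **The drift is hypothetical.** Variation that differs in direction between subjects is noise in a paired test, not bias; the rejection rates need a shift in a common direction. The documents give no evidence of one or of its size. Stating the acclimatization step for Day 0 only makes a Day 0 versus later shift conceivable, no more.
- **An occlusion estimate is not a stated aim,** and this is a pilot sized by feasibility. True, but the estimate comes from readings already planned.

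It is also tempting to convert the uncovered site to a second occluded control. That would give up the only drift reference, and any precision gain depends on assumptions about averaging and site variances that the documents do not supply.

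**Conclusion.** The point holds as a modest, cheap improvement to the secondary analyses of hydration and color. XI.1 gives the uncovered site no comparator role, so own-baseline changes at the treated and occluded sites confound drift with effect.

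The illustrated size, 9-29% rejection at n=10 and 28-93% at n=50 for drifts of 0.2-0.5 SD, rests wholly on assumed systematic drift, no real effect and alpha 0.05. It shows sensitivity and does not predict this study's error rate. The correction further assumes that drift is common to the sites of a location.

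A reader might infer that the primary comparison is biased. The documents do not show this: half-life comes from impedance, and the Z-pores formula and any intact-skin reference are not given.

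**What to change.** Add to XI.1, for hydration and color:

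1. Report each covered site's change from baseline net of the same-day change at that location's uncovered site, beside the unadjusted change, because the subtraction adds one site's noise.
2. Estimate the covering effect as the occluded-untreated change minus the uncovered-untreated change, by location and day.
3. Keep treated versus occluded-untreated as the needle contrast, and say that treated minus uncovered combines needle and covering effects.

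The cost is a few sentences and some extra table columns, with no new visits, subjects or measurements. The statistical cost is a wider interval for the net change where between-site correlation is below 0.5, which is why both versions should be shown. The uncovered site itself should stay as designed.
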